3.1.5 Follow-Up Phase

Clinicians Participating in Intervention: After CST, a set of actual family meeting encounters with these trained clinicians will be audio recorded and coded, ensuring there are 23 meetings with each category of person trained. We estimate a total of 28 meetings will need to be recorded in order to obtain 23 meetings with each discipline. Clinicians participating in the intervention will complete an online survey after the actual family meeting that they are observed participating in.

This survey will measure team member perception and satisfaction with collaboration. We will administer the modified Baggs CSACD-N tool to all clinician team members who participate in an actual encounter, which will capture each discipline's experience with collaboration with other team members and satisfaction with care decisions.

Clinicians Not Participating in Intervention: Consented non-participating clinicians will have their normal, scheduled family meetings. Actual family meeting encounters with these clinicians will be audio or video recorded and coded. Clinicians not participating in the intervention will complete the same online survey as those clinicians participating in the intervention after the observed actual family meeting.

Parent-patient Dyads Participating in the Survey or Interview After Intervention: Potential subjects will be screened using the protocol inclusion and exclusion criteria. Parent-patient dyads will be recruited into the study in person, over the phone, or via e-mail. The goal for enrollment will be up to 50 parent-patient dyads, with 30 evaluable parent-

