- *Demographics of clinician participants*: The following data will be collected regarding clinician subjects: discipline, age, gender, ethnicity, race, number of years in practice, estimated number of family meetings conducted in a week, estimated average time spent on conducting family meetings, previous experience with communication skills training.

- *Team member perception and satisfaction with collaboration:* The Baggs CSACD-N tool^{94,109} will measure team member perception and satisfaction with collaboration both pre and post-CST. Clinicians will rate their level of agreement for 9 items on a 7-point Likert-type scale from “Strongly disagree” to “Strongly agree.” This tool will capture each discipline’s experience with collaboration with other team members and satisfaction with care decisions.

Survey Measures for Parent-patient Dyads

- *Demographics of parent-patient dyads:* The following baseline data will be collected regarding parent-patient dyads: age, gender, ethnicity, race, education level, and health literacy.
- *Parental preference for decision making control:* The Control Preferences Scale for Pediatrics (CPS-P)¹¹³ is a 5-item sorting measure of parent preferences for participation in treatment decision making.
- *Parental anxiety and depression:* The Hospital Anxiety and Depression Scale (HAD)¹¹⁴ is a 14-item measure of depression and anxiety.
- *Parental post-traumatic stress:* The Impact of Event Scale-Revised (IES-R)¹¹⁵ is a 22-item measure of post-traumatic stress disorder.
- *Parental trust in medical team:* The Trust in Physician Scale¹¹⁶ is a 10-item measure of trust in physicians.
- *Parental satisfaction with decision-making:* The Pediatric Family Satisfaction with Care in the Intensive Care Unit (PFS-ICU 24)¹¹⁷ is a 24-item tool and will measure (1) satisfaction with care and (2) satisfaction with medical decision-making, modified for parents/caregivers of critically ill children. The Communication Assessment Tool-Team (CAT-T)¹¹⁸ is a 15-item tool that will measure patient perception of communication with the medical team and is adapted to team environments. A more complete outline of the survey is described below in the Appendix 11.14.

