To evaluate clinician behavior in actual meetings we will revise a content-based coding scheme for observable behaviors that reflect skills learned in the training. We will start with a coding scheme previously used in the VitalTalk studies given the significant overlap in learning goals^{29,121,122}. The small number of new codes added will measure engagement by the attending physician of team members from other disciplines, and adherence to elements of best practices in family meetings (e.g., facilitating introductions of participants, setting an agenda, and summarizing what was discussed in the meeting). Coders will be trained in the coding scheme using a manual with detailed definitions of all the codes. All coders will code 2 or 3 co-design encounters together to obtain a consensus. Coders will also be trained in the Medical Interaction Process System (MIPS) coding scheme. MIPS draws upon a patient-centered approach and codes individual utterances between providers and patients, allowing for coding of both content and affective information⁸⁰. Because multiple clinicians will participate in any meeting, acknowledgement of a skill will be attributed both collectively to the clinician team and to the individual from a specific discipline. For example, it may be the case that before CST only the social worker verbally expresses empathy, but post-CST attending physicians and bedside nurses also verbally express empathy in a meeting. This would be considered a change in clinician behavior if either more verbal expressions of empathy are made overall or if more clinicians from different disciplines make the same total number of verbal expressions of empathy. To evaluate if there are differences in clinician behavior pre and post-CST, coders will be blinded to whether an audio file was made prior to or after CST, and whether it was in a simulated or actual clinical encounter by playing files in a random order.

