- Speaking time will be analyzed by comparing the change in the number of words spoken by physicians versus parents speak in pre- and post-CICU TALC meetings using generalized linear regression with binomial link function controlling for the length of the meetings. Means and standard deviations will be calculated for the tool and t-tests will determine if significant differences exist for the two groups pre and post-CICU TALC.
- Elicitation of parental concerns and empathic response to parental emotion will be determined through quantitative coding. Each skill will be analyzed separately, using the cutoffs to identify skill proficiency as used by Back. Univariate relationship pre/post intervention by outcomes (Table 1)
  - If the outcomes (skills acquisition scores) are continuous and satisfies the normality assumptions, then t-tests will be appropriate to compare pre – intervention and post – intervention changes.

- If outcomes are continuous but not normally distributed, then a Wilcoxon Rank sum test will be appropriate to compare pre –intervention and post –intervention changes.
- If outcomes are binary (high vs low), then chi-square/fishers exact tests will be appropriate to compare pre –intervention and post –intervention changes.
- Similar statistical analysis will be performed to compare pre –intervention and post –intervention changes overall and for each type of participant.
- Analyses will be presented at the meeting-level as well as the participant-meeting level. Participant-meeting level data will be stratified by physician-type pending  $\geq 5$  participants in the pre- and post-intervention groups for each type.
- Relationship pre/post intervention by outcomes adjusted for participant and meeting level characteristics
  - If sample size allows and there are significant univariate associations, we will utilize mixed effect regression models to explore the relationship between the intervention and outcomes, first controlling for--gender and years of experience and accounting for correlation of repeated measurements within participants. If sample size allows, we will include other characteristics including number of participants at the meeting, proportion of speaking time by participant type, etc

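### The SAP's exploratory skill model has no meeting effect and no discipline term, so its pre/post standard error is too small if clinicians in the same meeting are correlated

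*SAP*

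**What the plan says.** The SAP (Aim 2c, Analytic Plan) compares skill outcomes before and after the intervention with univariate tests, then offers an adjusted analysis. That analysis is described as "adjusted for participant and meeting level characteristics". The model is a mixed-effects regression, "first controlling for--gender and years of experience and accounting for correlation of repeated measurements within participants". It is to be fitted only if the sample size allows and the univariate associations are significant, and its stated purpose is exploratory. A second set of covariates is optional: "If sample size allows, we will include other characteristics including number of participants at the meeting, proportion of speaking time by participant type, etc". Neither list names clinician discipline, and no random effect or clustering for the meeting is mentioned.

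Discipline does appear elsewhere in the SAP. The univariate comparisons cover "changes overall and for each type of participant". There is also a breakdown: "Participant-meeting level data will be stratified by physician-type pending" at least 5 participants of each type in both phases. Results are to be shown at meeting level as well as participant-meeting level.

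The protocol collects the variable from clinicians in observed meetings (5.1.1: "discipline, age, gender, ethnicity, race, number of years in practice"). For actual meetings, Protocol 6.3.2 plans a different model, a fixed-effects regression with a clinician identifier. The same section says that a team encounter generally has two or more clinicians.

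**The concern.** Repeated measurement runs in two directions here. One clinician appears in several meetings, and one meeting contributes several clinicians. The SAP model handles the first and not the second. The second matters more for the pre/post contrast, because every row from one meeting has the same phase. Clinicians in a meeting share the family, the case and the conversation. If that makes their scores alike, the model counts more independent information about phase than the data hold, and its intervals are too narrow.

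The omission of discipline raises a lesser question. If the mix of disciplines differs between phases and disciplines differ in how often they show a skill, part of the mix change can enter the pooled phase effect. The protocol's clinician fixed effects would absorb stable discipline differences. The SAP model does not carry them over and puts nothing in their place.

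**Working it through.** The documents give no ICC, standard deviation, power or discipline mix for this model, so there is no planned figure to reproduce. Two checks were made.

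**1. Meeting clustering**

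Inputs:
- Clinicians per meeting, m: Protocol 6.3.2 says generally at least 2 and gives no mean. Assumed values: 2 and 5.
- Within-meeting ICC: not given. Assumed values: 0.05, 0.10 and 0.20.
- Nominal two-sided level: 0.05 (Protocol 6.3.2).

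Phase is constant within a meeting, so:
- design effect = 1 + (m − 1) × ICC
- SE ratio (correct ÷ planned) = √(design effect)
- true level = 2 × [1 − Φ(1.96 ÷ SE ratio)]

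| m | ICC | Design effect | SE ratio | True level |
|---|---|---|---|---|
| 2 | 0.05 | 1.05 | 1.025 | 0.056 |
| 2 | 0.10 | 1.10 | 1.05 | 0.062 |
| 2 | 0.20 | 1.20 | 1.10 | 0.074 |
| 5 | 0.05 | 1.20 | 1.10 | 0.074 |
| 5 | 0.10 | 1.40 | 1.18 | 0.098 |
| 5 | 0.20 | 1.80 | 1.34 | 0.144 |

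The number of meetings does not enter the design effect. The result is the same for the SAP's 230 meetings per phase as for the protocol's 28.

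A null simulation agrees. It had 28 + 28 meetings, 5 clinicians each from a pool of 60, a participant ICC of 0.2, a continuous outcome and a participant random intercept only. Rejection at nominal 0.05 was 0.053, 0.088, 0.090, 0.145 and 0.190 at meeting ICC 0, 0.05, 0.10, 0.20 and 0.30. The model SE stayed at 0.124 throughout, while the empirical SE rose from 0.125 at ICC 0 to 0.168 at ICC 0.20 (0.168 ÷ 0.124 = 1.35, against 1.34 by formula).

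The remedy was tested in a separate simulation with the same numbers of meetings and clinicians. A crossed meeting intercept cut rejection from 14% to 6% at ICC 0.20 and from 11% to 7% at ICC 0.10. At ICC 0.20 the mean model SE rose from 0.112 to 0.154, against an empirical 0.151. At ICC 0 the added term widened the mean SE by only 2% to 3%.

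**2. Discipline mix**

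With no adjustment, bias = (shift in share) × (gap between disciplines). For an assumed shift of 10 to 20 points and an assumed gap of 0.5 to 1.0 SD, this runs from 0.10 × 0.5 = 0.05 SD to 0.20 × 1.0 = 0.20 SD. The participant random intercept absorbs part of it. The SAP model was simulated with 0, 50 or 100% of clinicians common to both phases and no meeting correlation:
- 28 + 28 meetings: bias 0.014 to 0.116 SD, rejection 0.04 to 0.09
- 230 + 230 meetings: bias 0.004 to 0.030 SD, rejection 0.00 to 0.07

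Adding a discipline term brought the bias to between −0.018 and +0.009 SD.

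**The case against.** Several points on the other side stand.

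- **The model is not the main analysis.** It is exploratory and doubly conditional, in a pilot.
- **Meeting-level results are also planned.** They do not have the within-meeting clustering problem.
- **Both consequences are conditional.** With an ICC of 0 the planned SE is right, and with 2 clinicians per meeting the inflation is modest.
- **Discipline is not ignored.** The by-type and physician-type results address it, and the open-ended covariate list leaves room for it. But those comparisons are univariate, the breakdown depends on 5 per type and may leave out nurses and social workers, and the open list commits to nothing.

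Stronger readings are tempting but unsupported:

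- **That the model cannot be fitted to parent speaking time because parents have no years of experience.** The SAP gives speaking time its own regression, adjusted for meeting length. It ties the comparisons that lead to the mixed model to skill scores, and it lists share of speaking time as a candidate covariate.
- **That the protocol treats discipline as the main driver of empathic speech.** The passage in 5.2.1 ("before CST only the social worker verbally expresses empathy") is a hypothetical example about attributing skills, and it counts spread across disciplines as genuine change.
- **That the post-phase recording rule (3.1.5, "ensuring there are 23 meetings with each category of person trained") shows the mix will shift.** No document gives the pre-phase mix to compare with.
- **That a mix shift would pass as a large skill gain.** Arithmetic on raw pooled rates can suggest this, but that is not what the planned model estimates.

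**Conclusion.** The point holds in a limited form. As written, the adjusted skill model understates the standard error of the pre/post effect whenever clinicians in the same meeting are positively correlated. At an assumed ICC of 0.10 to 0.20, the correct SE is 5% to 10% wider with 2 clinicians per meeting and 18% to 34% wider with 5. The corresponding true levels are about 0.06 to 0.07 and 0.10 to 0.14. These figures rest on the assumed ICC and number of clinicians, on equal meeting sizes, and on a normal approximation.

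The missing discipline term is secondary. If the mix shifts between phases, the residual bias is usually small. Whether it shifts cannot be told from the documents.

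The change is still worth making. The variables are collected, and Protocol 6.4 looks ahead to a stepped-wedge study, for which honest precision from the pilot matters.

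**What to change.** In the SAP's adjusted model for skill outcomes at the participant-meeting level:

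1. Add a meeting random intercept crossed with the participant intercept. State that meeting-clustered standard errors will be used if the crossed model does not converge.
2. Include clinician discipline as a fixed covariate in the pooled model. This does not remove the spread of skills across disciplines that Protocol 5.2.1 counts as change: a nurse who begins to express empathy still contributes. It removes only the effect of who attended.
3. Reconcile this model with the clinician fixed-effects regression in Protocol 6.3.2 and 6.4, and say which one governs. The fixed-effects model has no meeting term either, and it estimates the phase effect only from clinicians recorded in both phases.

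The number of clinicians present need not be forced into every model. It can stay an optional covariate, as the SAP has it. The pre-meeting worksheet prompts teams to settle who will attend (Protocol 3.1.2), so attendance may be part of the intervention's effect.

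The cost is a change of wording with no new data collection, a few degrees of freedom for discipline, and somewhat wider intervals where within-meeting correlation exists.

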## Statistical Analysis Plan

Aim 2: Pilot test the co-design-adapted CICU TALC with CICU parents and clinicians to determine:

a) Acceptability of intervention: Hypothesis: Respondents will endorse above a critical threshold of acceptability on satisfaction instruments to 20 clinicians and 23 parents and in semi-structured interviews.

Analytic plan: A constructivist grounded theory approach will guide qualitative analysis of interview transcripts regarding acceptability of the intervention. Descriptive statistics will be calculated for quantitative data from the acceptability survey.

b) Feasibility of enrollment and data collection, and fidelity: Hypothesis: Feasibility will be defined by: i) 30% parental and 50% clinician enrollment and consent rates, and 80% subject retention, and attrition; ii) ability to collect outcomes data from 46 patients (CICU length of stay), from 46 parents and from 50% of eligible team members. and iii) intervention fidelity with 95% of enrolled parents and clinicians receiving parent-directed and team-directed interventions.

Analytic Plan: Data completeness and accuracy will be monitored. I will calculate descriptive summaries including means and standard deviations for continuous variables, and proportions for categorical variables. As appropriate for pilot trials, analyses will focus on estimating proportions of binary feasibility and fidelity endpoints and constructing 95% CIs. Analyses of parent-reported outcomes will primarily be descriptive. Means and standard deviations along with 95% confidence intervals will be calculated.

c) Impact of CICU TALC on CICU parent and team behavior in family meetings. Hypothesis: the intervention will increase parent speaking time by 60%, elicitation of parental concerns to 40%, and response to parental emotion by 30%. I will audio record 230 CICU family meetings occurring before CICU TALC is initiated and 230 after initiation and use quantitative methods to measure pre-vs-post differences in a) speaking time of parents and physicians; b) elicitation of parental concerns; and c) response to parental emotion.

Analytic Plan:

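### A late exploratory step of the SAP's Aim 2c models would adjust for speaking-time share, itself an Aim 2c outcome, so for the skill outcomes the coefficient would no longer be the total intervention effect

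*SAP*

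**What the plan says.** SAP Aim 2c sets out to "measure pre-vs-post differences in a) speaking time of parents and physicians; b) elicitation of parental concerns; and c) response to parental emotion". Its hypothesis is a 60% rise in parent speaking time, elicitation of concerns reaching 40%, and a 30% increase in response to emotion. The SAP plans 230 recorded meetings before the intervention and 230 after.

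Speaking time has its own analysis. Words spoken by physicians and by parents are compared "using generalized linear regression with binomial link function controlling for the length of the meetings", which in effect models a share of speech. Protocol sections 6.2 and 6.3.2 also treat minutes spoken by each discipline as a pre/post measure of team function.

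The SAP's comparisons for Aim 2c are then staged:

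1. Unadjusted pre/post tests (t, Wilcoxon rank sum, chi-square or Fisher).
2. Exploratory mixed-effects models, run under this condition: "If sample size allows and there are significant univariate associations". They begin with clinician gender and experience as covariates and allow for repeated measurements on the same participant.
3. Under a second sample-size condition, "we will include other characteristics including number of participants at the meeting, proportion of speaking time by participant type, etc".

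No text limits the step 3 covariates to particular outcomes, rules out speaking share when speaking time is the outcome, or describes the step as a mediation analysis.

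**The concern.** A covariate in a model for an intervention effect should be something the intervention cannot change. Speaking share is measured in the same meeting as the skill scores, and the SAP's own hypothesis is that the intervention shifts it. Holding it fixed asks how skill differs between phases among meetings with the same division of talk. That is not the effect of introducing the intervention. At best it is a direct effect, and only if nothing unmeasured (the difficulty of the meeting, for example) drives both speaking share and skill. The SAP does not state that assumption.

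What is at stake is interpretation. These models run only after a significant univariate association, so a likely use is to ask whether that association survives adjustment. With speaking share in the model, a real effect could appear to shrink or vanish because part of it was adjusted away. If the relation runs the other way, the effect could appear larger than it is.

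**Working it through.** The SAP states no figure for this adjustment, so there is none to reproduce. The check has a structural part and an illustration.

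**Structure.** Write T for phase (0 before, 1 after), M for parent speaking share in SD units, and Y for a skill score.

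- M = a·T + u, where a is the shift in share caused by the intervention.
- Y = d·T + b·M + e, where d is the direct effect and b the relation of share to skill.
- Without M in the model, the coefficient of T is the total effect, d + a·b.
- With M in the model, the coefficient of T is d.

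The difference is a·b. It contains no sample size, so more meetings do not reduce it. It is zero only if a = 0, which contradicts the SAP hypothesis, or b = 0.

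**Inputs.** From the SAP: a 60% relative rise in parent speaking time (applied here to share) and 230 meetings per phase. Assumed, because the documents do not give them: baseline parent share p0 from 0.10 to 0.30, SD of share from 0.08 to 0.12, d = 0.3 SD, and b from −0.3 to 0.5. Then a = 0.6·p0/SD.

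**Total effect, 0.3 + a·b. The adjusted effect is 0.30 in every cell.**

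| p0, SD | a | b = −0.3 | b = 0 | b = 0.3 | b = 0.5 |
|---|---|---|---|---|---|
| 0.10, 0.12 | 0.06/0.12 = 0.50 | 0.15 | 0.30 | 0.45 | 0.55 |
| 0.20, 0.12 | 0.12/0.12 = 1.00 | 0.00 | 0.30 | 0.60 | 0.80 |
| 0.30, 0.08 | 0.18/0.08 = 2.25 | −0.375 | 0.30 | 0.975 | 1.425 |

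- b positive: the adjusted effect is 0.30/0.45 = 0.67 of the total at the mild end and 0.30/1.425 = 0.21 at the strong end.
- b zero: no change.
- b negative: the adjusted effect of 0.30 exceeds a total that lies between −0.375 and 0.15.

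A least-squares simulation with 230 meetings per phase and 400 replicates per setting agrees. For b = 0.3 to 0.5 the adjusted effect was 0.22 to 0.66 of the total. At b = −0.3 it was about 0.30, against totals from −0.37 to 0.15.

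**If speaking time is the outcome.** Suppose two participant types account for all the speech. Then parent share = 1 − clinician share. A linear model of parent share that contains clinician share fits perfectly and leaves nothing for T. The simulated coefficient of T was 0.0000 in all 24 settings.

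**The case against.** The strongest reply is that little depends on this step. It is the last of three, it is exploratory, and it sits in a pilot. It follows a significant univariate association and two separate conditions on sample size. The unadjusted tests and the gender and experience model come first and do not contain the covariate. All of this stands and limits the weight of the point. It is not a reason to keep the covariate.

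Three stronger readings are tempting, and the documents do not support them.

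- *The adjustment biases the result towards no effect.* Attenuation is plausible, since the SAP expects speaking time and skills both to rise. But neither document says how speaking share and skill are related within meetings. The covariate also covers clinicians' shares, whose relation to skill could have either sign.
- *The SAP puts its speaking-time outcome on both sides of a model.* Speaking time has its own bullet and its own model. The block before the adjusted models concerns elicitation and empathic response, and describes the outcomes as skill scores. The adjusted models may therefore cover skills only. The text leaves this open, so circularity is conditional on the wider reading.
- *Power collapses.* One could reach this by taking the 23 post-training meetings of protocol section 3.1.5. The SAP text at issue plans 230 per phase, and any power figure would also have to reflect that the model runs only after a significant univariate result. The point concerns what is estimated and does not need a power figure.

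**Conclusion.** The point holds in a limited form. For elicitation of concerns and empathic response, a model containing speaking-time share does not estimate the total intervention effect. This follows from the SAP's own text, because the covariate is a named outcome with a hypothesised 60% change.

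The size is unknown. The range of about 0.2 to 0.7 of the total effect rests on the assumed baseline share, SD, direct effect and a positive relation between share and skill. With no relation there is no change, and with a negative one the distortion reverses. Circularity arises only if the models are also run on speaking time. The earlier steps of the analysis are untouched, so the correction is worth making before the adjusted models are run, but it does not threaten the main Aim 2c comparisons.

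**What to change.** In the last bullet of the SAP, delete the item on speaking-time share from the covariates of any model that estimates the intervention effect. State that adjustment is limited to characteristics the intervention cannot change, such as clinician gender and years of experience. Also state which outcomes the adjusted models cover, which settles the circularity question.

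The number of participants at the meeting needs the same test before it is kept. Protocol section 3.1.2 describes a pre-meeting worksheet, part of the training, that has clinicians identify who will attend, so attendance may itself respond to the intervention. For the same reason, planned attendance is not automatically a safe substitute.

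If the route through speaking share is of interest, report it separately as an exploratory mediation analysis, labelled as such and with its assumptions stated.

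The deletion removes one phrase and needs no new data. The clarifications add a sentence or two to the SAP.
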